**Table 2-1 Protocol deviation codes and analysis sets**

Category Deviation code	Text description of deviation	Data exclusion
Participants are excluded from specified analysis sets		
INCL01A	Signed informed consent not obtained	Exclude participants from all analysis sets
INCL06	Subjects not meeting positive DBPCFC at screening	Exclude participants from PD analysis set
OTH33	ICH-GCP non-compliance	Exclude participants belonging to these sites from PK analysis set and PD analysis set
EXCL07	Participant has current or previous history of a mast cell disorder, including macrocytosis or tryptase > or = 20 ng/ml	Exclude participants from PD analysis set
Participants are not excluded from analysis sets, but data being impacted by protocol deviation is treated as missing value:		

Category Deviation code	Text description of deviation	Data exclusion
TRT12	Each dose (peanut/pacebo) administration at DBPCFC was not separated by at least minimum of 15 minutes	DBPCFC results will be treated as missing values for efficacy analysis
OTH20	DBPCFC stopped though participant did not experience any Dose Limiting Symptoms	DBPCFC results will be treated as missing values for efficacy analysis
OTH24	The sequence of the amounts of 1 mg, 3 mg, 10 mg, 30 mg, 100 mg, 300 mg, 600 mg, 1000 mg, and 3000 mg of peanut protein and corresponding placebo was not followed at end-of-treatment DBPCFCs	DBPCFC results will be treated as missing values for efficacy analysis

Any updates to the above table will be updated via SAP amendment prior to final DBL as required.

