### 12.8 Sample size calculation

A total of 72 participants will be enrolled in this study. The discontinuation rate is expected to be around 10%. Assuming an approximately 2:2:2:1:1 randomization ratio (2:1 ratio between 1-month remibrutinib treatment arms vs 1-week remibrutinib treatment arm and placebo arm), the anticipated number of completers in each of the remibrutinib 1-month treatment arms is expected to be around 14 to 16 participants and 7 to 8 in the 2 remaining arms.

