#### **16.4.3 Dosing Schedule**

No.	Peanut Protein/Placebo (mg)	Cumulative Dose (mg)
1	1	1
2	3	4
3	10	14
4	30	44
5	100	144
6	300	444
7	600	1044
8	1000	2044
9	3000	5044

After each administered dose of allergen (or placebo) participants are to be monitored for any reaction. In the presence of an allergic reaction, and at the investigator's discretion, the interval between escalating doses can be increased or the challenge can be stopped. ([Section 16.4.5](#)).

The minimum observation time between doses is 15 minutes, the maximum observation time is 30 minutes. If needed, an additional 30 minutes of observation is permitted for further evaluation of symptoms. If continuation of the DBPCFC is still in question after 1 hour of observation, the challenge should be considered positive and should be stopped.

During and up to at least one hour after the completion of the DBPCFC, vital signs should be monitored at minimum:

- Start of challenge
- End of challenge
- With administration of epinephrine or any rescue medications
- Vital signs should be taken every 15 minutes after dosing for up to at minimum 1 hour after last dose of rescue medication(s)
- At any time deemed clinically necessary or relevant

Additionally, the participant should be, at minimum, observed every 15 minutes by a study team member after the last dose is given for signs and symptoms of reaction as well as AEs. These observation findings should be documented in source documents.

In the event of an allergen dosing error, the site should contact Novartis.

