#### Primary endpoint – Responder rate

The statistical analysis will be based on the PD analysis set.

The null hypothesis of a no dose-response relationship for responder rate will be tested at a significance level of 10% against the one-sided alternative hypothesis of a dose-response relationship using the MCP-Mod methodology (Bretz et al 2005, Pinheiro et al 2014).

The primary endpoint will be analyzed based on logistic regression model, including treatment arm as a categorical variable (all remibrutinib doses and placebo) and including, but not limited to, log-transformed baseline total IgE and baseline tolerated peanut allergen dose as covariates. The logistic regression model is defined as follows. The response  $y_{ij}$  for subject  $i$  in dose group  $j$  receiving dose  $d_j$  is modelled as  $y_{ij} \sim \text{Bin}(1, p_{ij})$  with  $p_{ij} = \text{logit}^{-1}(\delta_j + x_{ij}^T \beta)$ , where  $x_{ij}$  are covariates of subject  $i$  in dose group  $j$ ,  $\delta_j$  are dose-specific intercepts and  $\beta$  are parameters associated with the covariates, common across dose groups. Any missing values in the covariates will be replaced with the median value for that variable. All covariates will be standardized to have a mean of 0 and a standard deviation of 0.5, so they are on the same scale as the binary input (Gelman, 2008).

In case of complete separation, the Maximum Likelihood estimate of the logistic regression does not exist. If this problem is encountered, we will replace the logistic regression by a Bayesian logistic regression with weakly informative priors. The Bayesian logistic regression model follows the same model equation as above, but incorporates weakly informative priors for the model's parameters. Priors are specified as follows: for parameters associated to the

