## 3 Sample size calculation

The primary objective of this study is to characterize the dose-response relationship among remibrutinib doses (CCI) and placebo with respect to the primary endpoint, responder rate after one month of treatment. The sample size was determined with DesignMCPMod (v0.1.2) application

Approximately 14 completers per remibrutinib 1-month treatment arm and 7 completers on the placebo arm provides at least 80% power (power over the different chosen candidate models assumed) to detect a dose-response relationship for a one-sided alpha of 10%, assuming a true maximum treatment effect of CCI responder rate and placebo treatment effect of CCI responder rate.

CCI

CCI

CCI

Table 3-1

CCI

CCI

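### SAP Table 2-1 voids the challenge result even when 600 mg has already been tolerated, so participants who meet the primary responder definition can be dropped from the primary analysis

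*SAP*

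**What the plan says.** - **Endpoint.** SAP 1.2.1 and 2.5.1 define a responder as someone who tolerates a single dose of at least 600 mg of peanut protein (1044 mg cumulative) without dose-limiting symptoms. The summary measure is the difference in responder proportions.
- **Dose ladder.** Protocol 16.4.2.1 and 16.4.3 give nine end-of-treatment doses. The seventh is 600 mg; 1000 and 3000 mg follow it.
- **Deviation rule.** SAP Table 2-1 keeps three kinds of participant in the analysis set but voids their data: OTH20, "DBPCFC stopped though participant did not experience any Dose Limiting Symptoms"; TRT12, "Each dose (peanut/pacebo) administration at DBPCFC was not separated by at least minimum of 15 minutes"; and OTH24, where the dose order was not followed at end of treatment. The consequence is the same for all three: "DBPCFC results will be treated as missing values for efficacy analysis".
- **Primary analysis.** SAP 2.5.3 uses completers only and takes dropout to be completely at random.
- **Other analyses.** The one sensitivity analysis (SAP 2.5.4) concerns prohibited medication. In SAP 2.5.5, supplementary estimands 1 and 3 (multiple imputation) will not be run. Estimand 2 scores a missing challenge as non-response, apart from public health emergencies. Estimand 4 uses reactions on the placebo day.
- **Unresolved challenges.** Protocol 16.4.3 states: "If continuation of the DBPCFC is still in question after 1 hour of observation, the challenge should be considered positive and should be stopped".

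**The concern.** The endpoint and the data rule do not fit together. Once 600 mg has been tolerated, with 1044 mg cumulative, nothing later in the challenge can change primary responder status. Table 2-1 nevertheless voids the result if the participant then stops without symptoms, or if a spacing or order fault occurs only at a later step. Only someone who reached 600 mg can lose a result in this way, so the loss is tied to response.

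At stake are the responder proportions, the risk difference and the dose-response estimates built on them, in arms planned at 14 and 7 completers. No retained analysis restores the voided results. Estimand 2 does not say how it treats them, so it could score a proven responder as a failure.

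**Working it through.** **The plan's own figure.** Protocol 12.8: "A total of 72 participants will be enrolled in this study", allocated 2:2:2:1:1, with about 10% discontinuation.
- 72 × 2/8 × 0.9 = 16.2 and 72 × 1/8 × 0.9 = 8.1. These match the upper ends of the stated 14 to 16 and 7 to 8 completers.
- SAP 3 bases power on the lower ends: "Approximately 14 completers per remibrutinib 1-month treatment arm and 7 completers on the placebo arm". From 18 and 9 randomised, that is a loss of 22% (1 − 14/18).
- No sample-size figure is in dispute. The MCP-Mod power cannot be recomputed because its inputs are redacted.

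**Inputs for the bias.**
- Active rate 80% (Protocol, Amendment 02 rationale).
- Placebo rate 5%, assumed because the planning value is redacted. The visible rows of SAP Table 2-2 are 0/26 and 7/138.
- True difference 80 − 5 = 75 points; odds ratio (0.80/0.20)/(0.05/0.95) = 76.
- Deviation rates are not in the documents. Assumed: 5 to 30% of responders stop after 600 mg, or a 1 to 5% fault rate per between-dose gap.

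**Formula.** With true rate p and missing fractions mR (responders) and mN (non-responders):

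observed rate = p(1 − mR) / [p(1 − mR) + (1 − p)(1 − mN)]

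**OTH20 after 600 mg** (mN = 0, same mR in both arms). Example at mR = 0.10: active 0.72/0.92 = 78.3%, placebo 0.045/0.995 = 4.5%.

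| Responders voided | Active rate | Difference | Shift |
|---|---|---|---|
| 5% | 79.2% | 74.4 | −0.6 |
| 10% | 78.3% | 73.7 | −1.3 |
| 20% | 76.2% | 72.2 | −2.8 |
| 30% | 73.7% | 70.1 | −4.9 |

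If responders are lost only in the active arm (10, 20, 30%), the difference reads 73.3, 71.2 and 68.7 points, and the odds ratio falls to 68, 61 and 53.

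**TRT12 and OTH24**, constant fault rate q per gap, peanut day only. A participant who tolerates all nine doses has 8 gaps; one who reacts at 100 mg has 4. P(void) = 1 − (1 − q)^gaps.

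| q | Reactor at 100 mg | Full tolerator | Difference |
|---|---|---|---|
| 1% | 3.9% | 7.7% | 74.5 |
| 2% | 7.8% | 14.9% | 74.0 |
| 5% | 18.5% | 33.7% | 72.4 |

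These rows count faults at any step. In a full tolerator, the chance that the first fault follows the 600 mg dose is (1 − q)^6 × [1 − (1 − q)^2] = 1.9%, 3.5% and 7.2%. That is 21 to 24% of such a participant's voided results, and only this part concerns an outcome already known.

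**Opposite direction.** If OTH20 instead removes 10, 20 or 30% of eventual non-responders who stopped below 600 mg, the difference reads 76.1, 77.2 and 78.1 points, overstated by 1.1 to 3.1.

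**Scale.** The 80% half-width for 14 versus 7 is 1.28 × √(0.16/14 + 0.0475/7) = 17 points.

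**Illustrative arm of 14.** 11/14 = 78.6% becomes 9/12 = 75.0% if two determined responders are voided, or 9/14 = 64.3% if estimand 2 counts them as failures.

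**The case against.** The best defence is that the block heading in Table 2-1 speaks only of data affected by the deviation, so a sensible programmer would keep a result settled before the fault. That reading is possible, but the action column voids the challenge results with no such limit, and the SAP should not depend on a charitable reading.

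Several other objections stand in whole or part:
- The shift is small beside the sampling error. The odds ratio stays at 76 if missingness depends only on responder status, although the estimand's summary measure is the difference in proportions.
- The completely-at-random wording in SAP 2.5.3 is written for dropouts. Results voided by deviation leave the same analysis with no other handling, so the assumption is implicit for them.
- Voiding a result after a short gap before 600 mg is defensible, because it is unclear which dose caused a reaction.

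A reader might also infer stronger claims that the documents do not support:
- **The chance of being voided rises with the dose tolerated.** For TRT12 and OTH24 this needs an assumed constant fault rate per gap. For OTH20 it fails: someone who completes 3000 mg was not stopped.
- **A short gap on the placebo day erases the peanut result.** TRT12 names both materials, but its effect across days is ambiguous.
- **OTH20 deletes challenges that Protocol 16.4.3 counts as positive.** Stops that follow the protocol are not naturally deviations. The relation is unstated rather than shown to be wrong.

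**Conclusion.** The point holds in a limited form. As written, Table 2-1 discards primary outcomes that are already determined. The clearest case is OTH20 after 600 mg; TRT12 and OTH24 faults confined to later steps are the others. This missingness depends on the outcome and can bias the proportions and the risk difference.

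The size is conditional on deviations occurring. With an 80% active rate, an assumed 5% placebo rate and the assumed deviation ranges acting alike in both arms, the shift is about 0.5 to 5 points, usually towards no effect. It reaches 6.3 points (75 − 68.7) only if 30% of active responders and no placebo responders are voided. Stops below 600 mg leave status undetermined, and removing them could act the other way. The documents do not show that the primary analysis will be biased, nor by how much.

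**What to change.** Amend SAP Table 2-1 before final database lock, which the SAP's note to that table already allows. The work should be done by staff blinded to arm.

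1. Derive status separately at 600, 1000 and 3000 mg from the peanut doses validly given before the deviation.
2. Keep the result at a threshold if, before any deviation, the threshold dose and its stated cumulative dose were tolerated, or a dose-limiting symptom occurred at or before it. The cumulative condition is needed: skipping 300 mg gives 1 + 3 + 10 + 30 + 100 + 600 = 744 mg, short of 1044. Define when a dose counts as tolerated if the gap straight after it was short.
3. Set to missing only thresholds still undetermined at the deviation. Scoring early stoppers without dose-limiting symptoms as non-responders would be a choice of strategy and should not be built into the primary rule.
4. State that a placebo-day deviation alone does not void the peanut result for the primary endpoint. Placebo-day data stay in use for estimand 4.
5. State how estimand 2 treats voided results.
6. Reconcile OTH20 with the one-hour rule in Protocol 16.4.3.
7. Keep the present set-to-missing rule as a sensitivity analysis, and add best-case and worst-case analyses for undetermined results.

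The cost is SAP wording and a little more derivation work.

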#### **16.4.2.2 Maximum dose**

Within the DBPCFC, incremental allergen (or placebo) dose increases continue until the highest dose for the challenge has been reached or until the participant displays (a) dose-limiting symptom(s) ([Section 16.4.5](#)).

300 mg peanut protein is estimated to correspond to the amount of allergen generally associated with accidental exposure, while 3000 mg corresponds to the highest peanut protein dose used within this protocol.

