## 16.4.6 Evaluation parameters of the DBPCFC

Objective symptoms exhibited by participants should be evaluated through physical examination. Complaints arising from the participant without observable changes will be classified as subjective.

The DBPCFC will be **positive** with the occurrence of any dose-limiting symptom(s). Dose-limiting symptoms indicate a true allergic reaction occurring during administration of a single dose that should preclude the administration of any further doses. Investigators must adhere to [Table 16-6](#) (CoFAR grading scale) for definition of dose-limiting symptoms ([Chinthrajah et al 2022](#)). According to the CoFAR grading scale, symptoms are classified as mild, moderate or severe. Investigators must not deviate from the severity score when deciding to continue or discontinue the DBPCFC in order to ensure the precision of the procedure and to preserve the safety of the participants.

The DBPCFC is positive when the occurrence of any dose limiting symptom(s) is/are detected as below:

- Any moderate and severe symptom(s) as defined in [Table 16-6](#) (CoFAR grading scale)
- Any symptom(s) that require administration of any rescue medication (e.g., SABA, epinephrine or other)
- A combination of mild symptoms during a single dose as defined in [Table 16-6](#), at the discretion of the investigator

Once any of the dose limiting symptom(s) described above are observed, the next dose of DBPCFC must not be administered.

All findings that the investigator classifies as reactions to the DBPCFC should be recorded in source documentation and on a designated eCRF. These events should not be reported on the Adverse Event eCRF unless they constitute an SAE according to the investigator's judgement.

The details and start time of any treatment and/or medication provided to treat DBPCFC-related allergic reactions should be recorded on the respective eCRF. The DBPCFC will be considered **negative** if a participant does not exhibit dose-limiting symptom(s) by the end of the challenge.

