### 1.2.1 Primary estimand(s)

The estimand is the precise description of the treatment effect and reflects strategies to address events occurring during trial conduct which could impact the interpretation of the trial results (e.g. premature discontinuation of treatment). The primary clinical question of interest is to understand the treatment effect of remibrutinib over placebo among participants who have completed actual DBPCFC after one month (4-5 weeks) of treatment and regardless of intake of rescue medication prior to actual DBPCFC at one month.

The primary estimand is described by the following attributes to address the primary clinical question of interest:

- Population:** Participants aged 18 – 55 years, inclusive, who have been diagnosed with IgE-mediated confirmed peanut allergy and met study inclusion/exclusion criteria and have undergone actual DBPCFC (2A & B) at one month (4-5 weeks).
- Variable:** Responder status defined as tolerating a single dose of  $\geq 600$  mg (1044 mg cumulative tolerated dose) of peanut protein without dose-limiting symptoms during the DBPCFC conducted at one month (4-5 weeks). The cumulative tolerated dose is the sum of the tolerated doses, not including the reactive dose. Dose-limiting symptoms indicate a true allergic reaction occurring during administration of a single dose of peanut protein at the

actual DBPCFC that should preclude the administration of any further doses in the view of the investigator.

- **Treatment:** The randomized treatment (one of five arms specified in [Section 2.1.1.1](#)) plus rescue medication (e.g., epinephrine, short-acting beta agonist, and/or anti-histamines) prior to actual DBPCFC at one month, if needed.
- **Intercurrent events:**
  - Discontinuation of treatment prior to the End of Treatment Assessments on Days 25, 26 and 28: Participants who discontinue treatment prior to actual DBPCFC, or who miss more than 20% of treatment doses throughout the study, or who miss medication doses for  $\geq 3$  consecutive days in the seven days prior to the one month actual DBPCFC part 2A due to any reasons other than adverse events
  - Intake of rescue medication prior to the actual DBPCFC
- **Summary measure:** Difference in the proportion of responders between remibrutinib and placebo

Supplementary estimands to the primary estimand are defined in [Section 2.5.5](#).

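### SAP code OTH20 sets a symptom-free early stop to missing even when 600 mg has already been tolerated, so a known primary responder can be dropped

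*SAP*

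**What the plan says.** SAP Section 2.2, Table 2-1, has a block of deviations that leave the participant in the analysis sets but set the affected data to missing. Code OTH20 in that block reads "DBPCFC stopped though participant did not experience any Dose Limiting Symptoms", with the consequence "DBPCFC results will be treated as missing values for efficacy analysis". The row does not mention the dose reached, the reason for the stop, or whether it concerns the peanut or the placebo day. The note under the table says "Any updates to the above table will be updated via SAP amendment prior to final DBL as required".

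The primary endpoint (SAP 2.5.1) is tolerating a single dose of at least 600 mg. On how the tolerated dose is counted, SAP 1.2.1 states: "The cumulative tolerated dose is the sum of the tolerated doses, not including the reactive dose". The end-of-treatment challenge goes on to 1000 mg and 3000 mg (protocol 16.4.2.1 and 16.4.3). Protocol 16.4.2.2 requires escalation to continue to the top dose or to dose-limiting symptoms, so a symptom-free stop before 3000 mg is a deviation.

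The primary analysis (SAP 2.5.3) uses completers and assumes that dropout is completely at random. Supplementary estimand 2 (SAP 2.5.5) counts a missing challenge as non-response, except where a public health emergency caused it. Supplementary estimands 1 and 3, which would have imputed missing outcomes, will not be run.

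**The concern.** The row discards the whole challenge, although the primary question may already be answered when the participant stops. Someone who tolerates 600 mg and declines the 1000 mg portion is a responder by definition, yet contributes nothing. Someone who takes the 1000 mg portion and reacts is kept as a responder. The milder experience is the one removed.

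For the primary endpoint, the known outcomes lost this way can only be responses, because a symptom-free stop before 600 mg leaves the outcome unknown. Removal of known responders is not removal completely at random. Nor is it the situation that SAP 2.5.3 describes, which is dropout and treatment discontinuation or interruption. No planned analysis restores the result: the sensitivity analysis in SAP 2.5.4 concerns prohibited medication. If a missing challenge in supplementary estimand 2 includes OTH20 results, that analysis counts a proven responder as a non-responder.

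At stake are the arm-level response rates that feed the dose-response fit, in arms of about 14 to 16 on active treatment and 7 to 8 on placebo.

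**Working it through.** **1. Which outcomes are known at the stop** (peanut challenge; steps 7, 8 and 9 are 600, 1000 and 3000 mg, protocol 16.4.3)

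| Course of the challenge | ≥600 mg | ≥1000 mg | 3000 mg | Under the plan |
|---|---|---|---|---|
| Symptom-free stop before 600 mg is tolerated | unknown | unknown | unknown | all missing (defensible) |
| 600 mg tolerated, symptom-free stop before 1000 mg | responder | unknown | unknown | all missing |
| 1000 mg tolerated, symptom-free stop before 3000 mg | responder | responder | unknown | all missing |
| 600 mg tolerated, dose-limiting symptoms at 1000 mg | responder | non-responder | non-responder | all kept |

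Rows 2 and 3 are the problem.

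**2. Arm sizes.** Protocol 12.8 gives 72 participants, allocation 2:2:2:1:1 and about 10% discontinuation. Completers: 72 × 2/8 × 0.9 = 16.2 per one-month active arm and 72 × 1/8 × 0.9 = 8.1 on placebo. These match the upper ends of the stated 14 to 16 and 7 to 8. The power statement uses the lower ends, 14 and 7.

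**3. One affected active participant** (the count is an assumption). The arm rate is set near the 80% in the Amendment 02 rationale, with r responders among n.

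- Primary analysis, (r−1)/(n−1) − r/n:
  - n = 14: 10/13 − 11/14 = 76.9% − 78.6% = −1.6 points
  - n = 16: 12/15 − 13/16 = 80.0% − 81.25% = −1.25, about −1.3 points
- Estimand 2, if OTH20 counts as a missing challenge, (r−1)/n − r/n:
  - n = 14: 10/14 − 11/14 = −7.1 points
  - n = 16: 12/16 − 13/16 = −6.25, about −6.3 points

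For scale, the standard error of one arm at 11/14 is √(0.786 × 0.214/14) = 11.0 points, so a difference between two such arms has standard error 11.0 × √2 = 15.5 points. The −1.6 points is about 0.1 of that.

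**4. A share f of responders stopping after 600 mg** (f assumed). The observed rate is p(1−f)/(1−pf). At p = 0.80 it is 79.2%, 78.3% and 76.2% for f = 5%, 10% and 20%.

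**5. Placebo arm of 7.** With one responder, losing that person moves 1/7 = 14.3% to 0/6 = 0%. The difference from an active arm at 11/14 then rises from 64.3 to 78.6 points. This requires a placebo responder who also stops early. At an assumed 5% placebo rate, the chance that any responder exists is 1 − 0.95^7 = 30%. The chance that one exists and stops early is 1 − (1 − 0.05f)^7 = 1.7%, 3.4% or 6.8% for f = 5%, 10% or 20%.

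**6. Overall test.** Doses, model shapes and placebo rate are redacted, so the MCP-Mod contrast cannot be reproduced. As a crude proxy, one-sided Fisher p-values are:

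| Active arm | vs 0/7 | vs 1/7 |
|---|---|---|
| 11/14 (all kept) | 0.0010 | 0.0090 |
| 10/13 (responder dropped) | 0.0016 | 0.0124 |
| 10/14 (responder recoded) | 0.0028 | 0.0209 |

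All are well below the one-sided 10% level.

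**The case against.** **Completers.** SAP 1.2.1 frames the clinical question among participants who completed the challenge, and SAP 2.5.3 defines a completer in the same terms. Someone who quits after 600 mg is arguably not one. This is a possible reading, but the population attribute in SAP 1.2.1 asks only that the participant has undergone both parts of the one-month challenge.

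**Affected data only.** The block heading in Table 2-1 limits the loss to data that the deviation affects, and a stop before 1000 mg does not affect the 600 mg result. That would be the sensible outcome, but the OTH20 row states its consequence without limit. Two defensible derivations of a primary endpoint should be settled before lock.

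**Size.** Deviation counts will be tabulated (SAP 2.3.1), there may be none of this kind, and dropping an active responder lowers the active rate, which is usually conservative. All of this stands. It limits the severity but does not make the rule right.

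**A stronger reading that a reader might infer.** Protocol 16.4.3 says: "If continuation of the DBPCFC is still in question after 1 hour of observation, the challenge should be considered positive and should be stopped". Protocol 16.4.6 adds: "Investigators must not deviate from the severity score when deciding to continue or discontinue the DBPCFC". One could conclude that OTH20 also voids one-hour stops, removes known non-responders and so inflates active response rates. The documents do not support this. Section 16.4.3 declares such a stop positive, and it complies with the protocol. Section 16.4.6 lets the investigator treat a combination of mild symptoms as dose-limiting, and SAP 1.2.1 leaves the judgement that a reaction should preclude further doses to the investigator. OTH20 would not naturally apply. What remains is possible miscoding of a stop for a single mild symptom, which merits a clarifying line at most.

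**Conclusion.** The point holds as a minor drafting error in a rule that affects the primary endpoint. Followed as written, OTH20 removes participants who have already met the primary responder definition, and it also removes a known response at 1000 mg when the stop comes before 3000 mg. Each affected active participant costs about 1.3 to 1.6 points in the primary analysis. The 6.3 to 7.1 points under supplementary estimand 2 depend on a missing challenge there including OTH20 results. The placebo shift is large per person but needs an uncommon combination of events.

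These sizes rest on an assumed single case and an active response rate near 80%; the documents give no frequency for such stops. A reader might infer that the primary test is in doubt or that the rule favours remibrutinib. Neither follows: the proxy p-values stay well below 0.10, and the loss of an active responder works against the drug, although the loss of a placebo responder would work for it. Setting the primary endpoint to missing remains reasonable when a symptom-free stop comes before 600 mg is tolerated.

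**What to change.** Amend SAP Table 2-1 before final database lock, as the note under the table allows:

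- For the peanut challenge, an OTH20 stop sets a responder endpoint (≥600, ≥1000 or 3000 mg) to missing only if that endpoint's dose had not already been tolerated. Otherwise the participant is kept as a responder for that endpoint.
- Use the same derivation in supplementary estimand 2, so that an OTH20 stop does not turn a known responder into a non-responder.
- Optional clarification: a peanut-day stop under the one-hour rule of protocol 16.4.3 is a positive challenge and is not coded OTH20.

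The cost is a few lines of SAP text and a small amount of reprogramming. The first two changes use only the doses tolerated, which the responder endpoints already require. The optional line may need the reason for stopping; the eCRF is not among the documents, so whether that is captured cannot be confirmed here.
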